8.6.2.1. B7-H4 expression for Part 2 eligibility

Part 2 dose will evaluate PF-07260437 in participants with advanced or metastatic HR+ HER2- BrCa (Part 2A) and TNBC (Part 2C) with high B7-H4 expression to assess early signs of clinical efficacy. Reference sets will be immunostained at a CLIA-certified central laboratory with a B7-H4 LDT and the resulting H-scores will be ranked from low to high and divided into 3 equal tertiles. Patient samples with H-scores that fall within the highest tertile of the reference set will be deemed as high B7-H4 expressors. The arbitrary threshold for high B7-H4 expression may be modified based on emerging clinical data. An additional cohort of 20 participants with advanced or metastatic HR+ HER2- BrCa and TNBC will be enrolled in Part 2B. These patients will not be enrolled based on B7-H4 expression. Samples will be immunostained and evaluated retrospectively to further explore B7-H4 expression levels and clinical efficacy.

8.6.3. Peripheral Blood Sample Collection and Assessments

Peripheral blood and derivatives may be used to characterize cell phenotypes, measure soluble proteins, and analyze nucleic acids to support study objectives. Examples may include but are not limited to cytokines, cell free DNA, and germline DNA.

For cytokine and circulating markers to be analyzed at a central laboratory, one 5 mL blood sample will be collected to isolate serum for cytokine and circulating marker measurement. Baseline collection is required pre-dose on Cycle 1 Day 1. On-treatment samples for cytokine

and circulating markers measurement will be collected as described in the [SOA](#). These samples will be used to evaluate changes from baseline. If Grade ≥ 1 cytokine release syndrome is suspected, additional unscheduled samples should be collected to match clinically indicated safety cytokine samples.

The cytokines to be measured may include, but not limited to IFN- γ , TNF-a, IL-1b, IL-2, IL-4, IL-5, IL-6, IL-8, and IL-10. Additional exploratory circulating markers may also be evaluated to measure changes in immune activation after therapy.

For analysis of cell-free DNA, plasma will be isolated from 10 ml blood at C1D1 and upon disease progression. Analysis of circulating tumor DNA in these samples may be correlated with participant response to therapy.

A 2 ml whole blood sample will be collected at C1D1 for isolation of baseline germline DNA. This sample may be used to enable subtraction of germline DNA variants from somatic mutations that may be identified in tumor or cell-free DNA samples.

Instructions for sample collection, processing, storage, and shipment will be provided in the Laboratory manual.

8.6.4. T Cell Immunophenotyping

Blood samples of approximately 5 mL of whole blood samples will be collected for evaluation of T, B, and NK cell immunophenotyping as well as characterization of T cells for markers such as but not limited to Ki67, PD-1, HLA-DR and other indicators of proliferation, activation, and exhaustion after therapy. Samples will be collected at the times specified in the Schedule of Activities. Instructions for sample collection, processing, storage, and shipment will be provided in the Laboratory manual.

Samples may also be used for flow cytometry assay development. Samples used for this purpose will be retained in accordance with local regulations and if not used within this time frame, will be destroyed.

8.6.5. Retained Research Samples for Biomarkers

Not applicable as Retained Research Samples for Biomarkers are not collected in this study.

8.6.6. Soluble B7-H4 Assessment

Whole blood samples (approximately 3 mL) to provide a minimum of 1 mL serum for soluble B7-H4 assessment will be collected at the times specified in the [SOA](#). An additional soluble B7-H4/other factor sample should also be taken if CRS is suspected, and a sample is not already scheduled to be taken (eg, from Cycle 4 onwards). Instructions for sample collection, processing, storage, and shipment will be provided in the laboratory manual. Soluble B7-H4 levels will be determined by a ligand binding assay, and samples may be used for further evaluation of the bioanalytical method, as well as for other internal exploratory

purposes. Samples collected for this purpose will be retained in accordance with local regulations and if not used within this time frame, will be destroyed.

8.7. Immunogenicity Assessments

Blood samples of approximately 5 mL, to provide a minimum of 2 mL serum, will be collected for determination of ADA and NAb as specified in the [SOA](#). Instructions for the collection and handling of biological samples will be provided in the laboratory manual or by the sponsor. The actual date and time (24-hour clock time) of each sample will be recorded.

Samples collected for determination of ADA and NAb may also be used for additional characterization of the immune response and/or evaluation of the bioanalytical method, or for other internal exploratory purposes. These data will be used for internal exploratory purposes.

Genetic analyses will not be performed on these serum samples unless consent for this was included in the informed consent. Participant confidentiality will be maintained.

Samples will be analyzed using a validated analytical method in compliance with applicable SOPs. Samples determined to be positive for ADA may be further characterized for NAb.

The immunogenicity samples must be processed and shipped as indicated in the instructions provided to the investigator site to maintain sample integrity. Any deviations from the immunogenicity sample handling procedure (eg, sample collection and processing steps, interim storage, or shipping conditions), including any actions taken, must be documented, and reported to the sponsor. On a case-by-case basis, the sponsor may make a determination as to whether sample integrity has been compromised.

Any changes in the timing or addition of time points for any planned study assessments must be documented and approved by the relevant study team member and then archived in the sponsor and site study files but will not constitute a protocol amendment. The IRB/EC will be informed of any safety issues that require alteration of the safety monitoring scheme or amendment of the ICD.

8.8. Health Economics

Health economics/medical resource utilization and health economics parameters are not evaluated in this study.

9. STATISTICAL CONSIDERATIONS

Detailed methodology for summary and statistical analyses of the data collected in this study is outlined here and further detailed in the SAP, which will be maintained by the sponsor. The SAP may modify what is outlined in the protocol where appropriate; however, any major modifications of the primary endpoint definitions or their analyses will also be reflected in a protocol amendment.

9.1. Statistical Hypotheses

There will be no formal hypothesis testing in this study.

9.1.1. Estimands

9.1.1.1. Primary Estimand/Co-Primary Estimands

Primary Estimand (DLT) for Part 1:

DLT rate estimated based on data from DLT-evaluable participants during the DLT-evaluation period (28 days for regimen without priming; priming doses plus 2 full doses for regimen with priming) in Part 1.

Variable: Occurrence of DLTs. DLTs are defined in [Section 4.3.6](#)

Analysis population:

For the dose escalation without priming, DLT-evaluable participants defined as participants:

- who receive at least 1 dose of study treatment and experience DLT during the DLT-evaluation period (28 days),

OR

- who complete the DLT-evaluation period without DLT. Participants without DLTs who withdraw from study treatment before receiving at least 2 full doses of study drug for reasons other than treatment-related toxicity are not evaluable for DLT.

For the dose escalation with priming, DLT-evaluable participants defined as participants:

- who receive at least 1 dose of study treatment and experience DLT during the DLT-evaluation period (priming doses plus 2 full doses, eg, 42 days),

OR

- who complete the DLT-evaluation period without DLT. Participants without DLTs who withdraw from study treatment before receiving at least the priming dose and 2 full doses of study drug for reasons other than treatment-related toxicity are not evaluable for DLT.

Population-level summary measure: DLT rate defined as the number of DLT-evaluable participants with DLTs in the DLT-evaluation period divided by the number of DLT-evaluable participants in the DLT-evaluation period.

Primary Estimand for Parts 1 and 2:

Incidence of AEs estimated in the analysis population during the AE-evaluation period, defined as the time from the first dose to earliest of 28 days post last dosing date and day of new anti-cancer therapy-1 day.

Variable: Occurrence of AEs. AEs are defined in [Section 8.3](#).

Analysis population: Safety analysis set defined as participants who receive at least 1 dose of study treatment without regard to tolerability or duration of treatment.

Population-level summary measure: Incidence of AEs defined as the number of participants with AEs in the AE-evaluation period divided by the number of participants in the analysis population. AEs will be summarized by type, frequency, severity (as graded by NCI CTCAE version 5), timing, seriousness, and relationship to treatment.

9.2. Analysis Sets

For purposes of analysis, the following analysis sets are defined.

Participant Analysis Set	Description
Full Analysis Set (FAS)	All enrolled participants.
Safety Analysis Set (SAS)	All enrolled participants who receive at least 1 dose of study intervention. Unless otherwise specified the safety analysis set will be the default analysis set used for all analyses.
Per Protocol Analysis Set	All enrolled participants who do not have major protocol deviations during the course of the study
DLT Evaluatable Set	All enrolled participants who had at least 1 dose of study treatment and either experienced DLT or do not have major protocol deviations during the DLT observation period.
mITT Population	All enrolled participants who have received at least 1 dose of study medication; have a baseline assessment and at least 1 post baseline assessment;
PK Parameter Set	All enrolled participants treated who do not have protocol deviations influencing PK assessment and have sufficient information to estimate at least 1 of the PK parameters of interest.
PK Concentration Set	All enrolled participants who are treated and have at least 1 analyte concentration above the lower limit of quantitation.
Response Evaluatable Set	All enrolled participants who received at least 1 dose of study treatment and had adequate baseline disease assessment. Participants who discontinued early or died will be included.
Pharmacodynamic/ Biomarker Analysis Set(s)	The Pharmacodynamic/Biomarker analysis population is defined as all enrolled participants with at least 1 of the Pharmacodynamic/Biomarkers evaluated at pre and/or post dose.
Immunogenicity Analysis Set	The immunogenicity analysis set includes all enrolled participants who received at least 1 dose of study treatment and have at least 1 sample tested for ADA.

9.3. Statistical Analyses

Detailed methodology for summary and statistical analyses of the data collected in this study is outlined here and further detailed in a SAP, which will be maintained by the sponsor. The data will be summarized with respect to demographic and baseline characteristics, efficacy observations and measurements, safety observations and measurements, pharmacokinetic and biomarker measurements.

9.3.1. General Considerations

Unless otherwise specified, summaries will be presented by dose group and overall. Descriptive statistics, such as the mean, standard deviation, coefficient of variation, median, minimum, and maximum values, will be provided for continuous endpoints. The rates of binary endpoints will be provided along with the corresponding 2-sided 95% CIs using an exact method. Time-to-event endpoints will be summarized using the Kaplan-Meier method and displayed graphically when appropriate. Median event times and 2-sided 95% CIs for each time-to-event endpoint will be provided.

Further details will be provided in the SAP.

9.3.2. Primary Endpoints/Estimands/Analysis

Part 1

Determination of MTD will be performed using Per-protocol analysis set (evaluable for MTD). The dose escalation in Part 1 of the study will be guided by a Bayesian analysis of DLT data for PF-07260437. Dose toxicity is modelled using 2-parameter logistic regression for the probability of a participant experiencing a DLT at the given dose for the monotherapy and using BLRM model specifically developed for combinations separately for regimens with and without priming. A mixture of weakly informative prior distribution based on nonclinical/expert opinion information and a MAP prior based on historical data will be used to define the prior distribution for the PF-07260437 monotherapy dose escalation. The MAP prior for the logistic model parameters for this study is the conditional distribution of the parameters given the historical data.

After each cohort of participants, the posterior distribution for the risk of DLT for new participants at different doses of interest for PF-07260437 will be evaluated separately for cohorts with and without priming, taking into account the different DLT observation periods (28 days for the regimen without priming; priming doses plus 2 full doses for the regimen with priming). The posterior distributions will be summarized to provide the posterior probability that the risk of DLT lies within the following intervals:

Under-dosing:	[0, 0.16]
Targeted dosing:	[0.16, 0.33]
Overdosing:	[0.33, 1]

Dosing decisions are guided by the EWOC principal (Rogatko et al, 2007). A dose may only be used for newly enrolled participants if the risk of overdosing at that dose is less than 25%.

Recommendation from the BLRM, along with safety (AEs, SAEs), laboratory, PK, biomarker, and other relevant data, will be used at the time of each dose escalation and for MTD/RDE determination.

Prior distributions:

Weakly informative prior distributions based on pre-clinical/expert opinion information will be chosen for the logistic parameters for prior distribution in Part 1, see [Appendix 9](#).

A MAP approach will be used to derive the prior distribution for model parameters used in Part 1 with priming based on the data collected in Part 1 without priming. The MAP prior for the logistic model parameters for this study is the conditional distribution of the parameters given the historical data (Neuenschwander et al, 2010; Schmidli et al, 2014). MAP priors are derived from hierarchical models, which take into account possible differences between the studies. A full description of the application of the MAP approach to derive the prior distributions of the PF-07260437 model parameters is provided in [Appendix 9](#).

Starting dose:

The starting dose for the monotherapy PF-07260437 is SC injection 100 µg Q2W. This dose satisfies the EWOC criterion. A full assessment of the prior risk to participants is given in [Appendix 9](#).

Stopping criteria:

The sponsor estimates that the maximum number of participants in the Part 1 dose escalation portion of the trial is 40 participants. However, the actual number may be more or less based on observed PK and safety. The dose escalation will stop when the following criteria are met:

- At least 6 participants have been treated at the recommended MTD or RDE.
- The dose d for PF-07260437 satisfies 1 of the following conditions for the mono-escalation part:
 - The probability of target toxicity at dose d exceeds 50%, ie, $\Pr(0.16 \leq d \leq 0.33) \geq 50\%$, or
 - A minimum of 15 participants have been treated in Part 1.

Part 1 and Part 2

Incidence of AEs estimated in the safety analysis population during the AE-evaluation period, defined as the time from the first dose to earliest of 28 days post last dosing date and day of new anti-cancer therapy-1 day.

- **Variable:** Occurrence of AEs. AEs are defined in [Section 8.3](#).
- **Analysis population:** Safety analysis set defined as participants who receive at least 1 dose of study treatment without regard to tolerability or duration of treatment.
- **Population-level summary measure:** Incidence of AEs defined as the number of participants with AEs in the AE-evaluation period divided by the number of participants in the analysis population. AEs will be summarized by type, frequency,

severity (as graded by NCI CTCAE version 5), timing, seriousness, and relationship to treatment.

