4.3.6. Dose Limiting Toxicity (DLT) Definition

A participant is classified as DLT evaluable if they either 1) receive all the planned doses of the study intervention and have received all scheduled safety assessments during the DLT observation period or 2) have experienced a DLT. If a participant fails to meet these criteria, they may be replaced. The sole exception to criterion 1) is if the participant has missed a minority of safety assessments due to emergency situations (eg, site accessibility issues, inability to go to an external lab, etc). In such cases, the Dose Level Review Committee may judge the participant evaluable, depending on the abundance of the available data.

DLT observation period: For the purpose of dose escalation, the DLT observation period for SC or IV dosing without priming will be 28 days including laboratory results obtained on the morning of Day 29 in each participant. The DLT period for dosing with priming will extend to include the duration of priming doses and 2 full doses (eg, if a single priming dose is administered 2 weeks prior to the first full dose, the DLT evaluation period will be 42 days (14 days plus 28 days) including laboratory results obtained on the morning of Day 43 (C2D15).

Any of the following treatment-related AEs occurring during the DLT observation period that in the opinion of the investigator cannot be reasonably attributed to the participant's underlying disease, concomitant medications or preexisting conditions are considered DLTs. Severity of AEs will be graded according to CTCAE version 5.0, with the exception of CRS, which will be graded according to the ASTCT CRS Consensus Grading for CRS (Appendix 11). For those events involving a worsening of a baseline abnormality, a DLT must represent a clinically significant (in the opinion of the Investigator after discussion with the sponsor) shift from baseline.

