#### 2.1. Study Objectives, Endpoints and Estimands

##### 2.1.1 Primary Estimand(s)

###### Primary Estimand (DLT) for Part 1:

DLT rate estimated based on data from DLT-evaluable participants during the DLT-evaluation period (28 days for regimen without priming; 42 days for the regimen with priming (priming doses plus 2 full doses)) in Part 1.

Variable: Occurrence of DLTs.

Analysis population:

For the dose escalation without priming, DLT-evaluable participants defined as participants:

- who receive at least 1 dose of study treatment and experience DLT during the DLT-evaluation period (28 days),

OR

- who complete the DLT-evaluation period without DLT. Participants without DLTs who withdraw from study treatment before receiving at least 2 full doses of study drug for reasons other than treatment-related toxicity are not evaluable for DLT.

For the dose escalation with priming, DLT-evaluable participants defined as participants:

- who receive at least 1 dose of study treatment and experience DLT during the DLT-evaluation period (priming doses plus 2 full doses, eg, 42 days),

OR

- who complete the DLT-evaluation period without DLT. Participants without DLTs who withdraw from study treatment before receiving at least the priming dose and 2 full doses of study drug for reasons other than treatment-related toxicity are not evaluable for DLT.

Population-level summary measure: DLT rate defined as the number of DLT-evaluable participants with DLTs in the DLT-evaluation period divided by the number of DLT-evaluable participants in the DLT-evaluation period.

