## 6. ANALYSES AND SUMMARIES

### 6.1 Primary Endpoint(s)

#### 6.1.1 DLTs (Part 1)

Determination of MTD will be performed using Per-protocol analysis set (evaluable for MTD) as described above in [Section 3](#).

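### The MTD is to be determined on the Per-Protocol set, not on the DLT-evaluable participants of the primary estimand

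*Protocol*

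**What the plan says.** Protocol 9.3.2 sets the population for the MTD: "Determination of MTD will be performed using Per-protocol analysis set (evaluable for MTD"). SAP 3.1 has the same sentence, and SAP 6.1.1 has it again: "Determination of MTD will be performed using Per-protocol analysis set (evaluable for MTD) as described above".

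Protocol 9.2 defines the Per Protocol set as "All enrolled participants who do not have major protocol deviations during the course of the study"; SAP Table 1 agrees. The definition has no condition on dosing, on the DLT window, or on having had a DLT.

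The Part 1 primary estimand uses a different population. Protocol 9.1.1.1 has "DLT rate estimated based on data from DLT-evaluable participants during the DLT-evaluation period", and SAP 2.1.1 gives the summary measure as "DLT rate defined as the number of DLT-evaluable participants with DLTs in the DLT-evaluation period divided by the number of DLT-evaluable participants". Protocol 4.3.6 begins "A participant is classified as DLT evaluable if they either 1) receive all the planned doses of the study intervention", and its alternative limb is having experienced a DLT.

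A DLT Evaluable Set also exists. Protocol 9.2 admits dosed participants who "either experienced DLT or do not have major protocol deviations during the DLT observation period". No analysis section (Protocol 9.3, SAP 3 or SAP 6) names this set, and no set called evaluable for MTD is defined.

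**The concern.** The named set decides who enters the MTD determination, and the dose chosen in Part 1 goes to about 60 Part 2 participants. Per Protocol membership depends on the whole study, and treatment can last up to 2 years, so it need not be final when escalation and MTD decisions are made. Events that have nothing to do with the DLT window can then change the data set. Losing a DLT participant, or keeping non-completers as non-DLTs, lowers the modelled risk. Losing a non-DLT participant raises it.

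The set for the cohort-by-cohort BLRM runs is not named either. Protocol 4.3.5 refers only to DLT data at all tested doses, and SAP 5.2 names no set. The fallback in Protocol 9.2 is "Unless otherwise specified the safety analysis set will be the default analysis set used for all analyses".

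**Working it through.** **1. The two sets compared**

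| Participant | Per Protocol | DLT-evaluable |
|---|---|---|
| DLT in the window, major deviation at any time | Out | In |
| Cleared the window, major deviation later | Out | In |
| No DLT, left before the second full dose for a non-toxicity reason, no major deviation | In | Out |

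Major deviation is not defined in these documents, so the frequency of each row is unknown.

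**2. Size, by illustration.** The plan gives no figure to reproduce. The model and prior come from Protocol Appendix 9:

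logit π(d) = log α + β log(d/d\*), with (log α, log β) bivariate normal, means (logit p\*, 0), SDs (2, 1), correlation 0.

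The documents give no values for d\* or p\*; the model scenarios are in a Technical Supplement that was not available. Assumptions:
- d\* = 300, 900, 1800 or 2700 µg
- p\* = 0.10, 0.20, 0.25, 0.30 or 0.33, giving 4 × 5 = 20 settings
- data: 0/3 at 100 µg, 0/3 at 300 µg, 2/6 at 900 µg

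The posterior was found by numerical integration. Pr(DLT rate ≥ 0.33 at 900 µg), lowest to highest over p\*:

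| d\* (µg) | 2/6, all DLT-evaluable | 1/5, one DLT participant lost | 2/5, one non-DLT participant lost | 2/8, two non-completers kept |
|---|---|---|---|---|
| 300 | 0.349–0.406 | 0.147–0.197 | 0.456–0.516 | 0.197–0.241 |
| 900 | 0.252–0.359 | 0.091–0.162 | 0.337–0.461 | 0.138–0.209 |
| 1800 | 0.164–0.256 | 0.048–0.097 | 0.224–0.337 | 0.087–0.143 |
| 2700 | 0.137–0.219 | 0.037–0.077 | 0.188–0.290 | 0.072–0.121 |

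Crossings of the 25% limit:
- 2/6 to 1/5 falls below it in 11 of 20 settings: all ten at d\* = 300 and 900, and d\* = 1800 with p\* = 0.33. The setting d\* = 900, p\* = 0.10 is marginal, starting at 0.252.
- 2/6 to 2/8 falls below it in the same 11.
- 2/6 to 2/5 rises above it in 6 of 20: d\* = 1800 with p\* 0.20–0.30, and d\* = 2700 with p\* 0.25–0.33.

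The observed rate at 900 µg moves from 2/6 = 33% to 1/5 = 20%, 2/5 = 40% or 2/8 = 25%.

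**3. Is there a net bias?** If deviations are unrelated to DLT status, one random removal takes a DLT participant with chance 2/6 and a non-DLT participant with chance 4/6. The average is (2 × [1/5 value] + 4 × [2/5 value]) / 6. At d\* = 300, p\* = 0.10 this is (2 × 0.147 + 4 × 0.456) / 6 = 0.353, against 0.349. That is the largest shift, 0.0045 before rounding. So there is no systematic bias on average, but a single removal can change the result.

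**4. Two defects in the DLT-evaluable definitions**

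- *Priming.* SAP Table 1 requires all Cycle 1 and Cycle 2 dosing. In the single-priming example, C1D1 is Day 1 (priming), C1D15 is Day 15 (full dose 1), C2D1 is Day 29 (full dose 2), and the window ends on Day 42. C2D15 is Day 28 + 15 = 43 (full dose 3), after the window.
- *Early stopping.* For a participant without a DLT who stops early for treatment-related toxicity, the estimand text (Protocol 9.1.1.1, SAP 2.1.1) excludes only withdrawals for other reasons. Protocol 4.3.6 requires all planned doses, and SAP Table 1 requires 100% dosing.

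**The case against.** The strongest reply is that this is a mislabel. The qualifier after Per-protocol, the estimand, the cohort minimums stated in DLT-evaluable participants (Protocol 4.1, 4.3.5) and the replacement rule in 4.3.6 all suggest that DLT-evaluable participants were meant. That is probably right, but the text attaches the qualifier to a set with its own, different definition, and it does so three times.

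The illustration also has limits, and these stand. The 25% limit governs doses for new participants, whereas the criticised sentence governs the MTD. The target-interval probability at 900 µg is 0.20 to 0.47 across all 80 combinations, never the 50% in the stopping rule, and fewer than 15 participants are treated (12, or 14 in the 2/8 case). The figures therefore describe mid-escalation, and only if the same set is used there. A deviation after the dose has been chosen cannot undo that choice; it affects only a later re-analysis.

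Some toxicity-related early stoppers would already be DLTs under Protocol 4.3.6.2 (a delay of more than 2 weeks) or 4.3.6.3. That narrows the second definitional defect without removing it. Premedication is permitted in some circumstances after a reaction; permitted use would simply not be a deviation.

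**Conclusion.** The concern holds. As written, the MTD population contradicts the primary estimand and Protocol 4.3.6, and the SAP repeats the conflict instead of resolving it. One reclassified participant can move the modelled overdose probability across 25% in either direction, depending on the assumed data, d\* and p\*. The net direction is not established.

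Harm is limited. The BLRM is one input among several (Protocol 9.3.2), the Dose Level Review Committee weighs all relevant clinical data (4.3.8), late toxicities meeting the DLT definition count toward the MTD (4.3.7), DLTs are listed (9.3.5.2), and the reported DLT rate is already defined on DLT-evaluable participants. This should be fixed. Confidence in the textual conflict is high; the figures are illustrative only.

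**What to change.** In Protocol 9.3.2 and SAP 3.1 and 6.1.1, name the DLT Evaluable Set for both the BLRM and the MTD determination. A Per-Protocol run may stay as a sensitivity analysis.

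Define the set once, identically in Protocol 9.2 and SAP Table 1:
- every dosed participant with a DLT in the observation period, regardless of deviations or doses received; and
- participants without a DLT who completed the period, received the doses scheduled within it for their regimen, and had no major deviation in it, keeping the 4.3.6 exception for a minority of missed assessments.

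Keep the in-window deviation test, which both tables already contain. Protocol 6.1.1.1 and 6.8.3 restrict prophylactic premedication and primary prophylactic colony stimulating factors in that window; without the test, a participant given them against the protocol could count as a clean non-DLT.

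In SAP Table 1, replace the Cycle 1 and Cycle 2 dosing condition for priming with all doses scheduled within the regimen's DLT observation period. The sponsor should reconcile Protocol 4.3.6, the estimand text and SAP Table 1 with one sentence on whether a participant without a DLT who stops early for treatment-related toxicity is evaluable. The second limb above and the estimand text should then follow it.

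The cost is wording in Protocol 4.3.6, 9.1.1.1, 9.2 and 9.3.2 and in SAP 2.1.1, 3.1, 6.1.1 and Table 1. If the sponsor regards this as a major modification of the primary analysis, Protocol 9 requires an amendment, with IRB/EC approval. No extra participants or data are needed, and only one extra model run if the sensitivity analysis is kept.
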